 1. DATA COLLECTION
 2. DATA MANAGEMENT
 3. DATA CONFIDENTIALITY
14. PRACTICAL USE OF THE RESULTS
15. ETHICS
16. ANNEX
 1. ECHOCARDIOGRAPHY PROTOCOL
 2. SCINTIGRAPHY PROTOCOL
 3. DECLARATION OF HELSINKI

1. STUDY SUMMARY

Study title and code	Prognostic impact of cardiac amyloidosis in patients with severe aortic stenosis who underwent percutaneous implantation of an aortic prosthesis (AMY-TAVI)
Study type and design	Observational analytical of multicenter prospective cohorts.
Number and characteristics of patients	321 patients to whom a TAVI has been implanted by severe degenerative AoS.
Study duration	Recruitment period: All the consecutive patients to whom a non-invasive diagnostic study of amyloidosis (scintigraphy with tecnecio ⁹⁹ pyrophosphate and electrophoresis of proteins in the blood) and to whom a percutaneous aortic prosthesis for severe aortic stenosis has been implanted. Follow-up period: clinical and echocardiographic monitoring will be done before discharge, in consultation at three, six, twelve, and twenty-four months. Inclusion: 1 year Follow-up: 2 years Data analysis: 6 months Total: 3 years and 6 months
Events	Main event: cardiovascular events (cardiovascular death, stroke, heart attack), death from any cause, readmission for cardiac insufficiency, pacemaker implantation, functional assessment
Participating countries and centers	Various Spanish and international centers will be invited to participate.

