8. OBJECTIVES

8.1 PRIMARY OBJECTIVE

A multicentre prospective study of cohorts consisting of two cohorts from patients who have been implanted with percutaneous aortic prosthesis as treatment for the severe degenerative aortic stenosis and compare the overall mortality and that for

cardiovascular and admissions for heart failure in the 2-year follow-up of patients diagnosed with amyloidosis (by GT99 and EFP) versus those that do not have it.

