8.1 SECONDARY OBJECTIVES

1. As part of the hypothesis, we will analyze separately the impact of the presence of amyloidosis on the requirements of permanent pacing (permanent pacemaker implantation, pacemaker dependence, changes in the conduction system)
2. Determine the impact on the functional class (measured by using the 6-minute test) of the coexistence of TTR amyloidosis in patients with a TAVI implant.
3. Validate echocardiographic patterns of cardiac amyloidosis diagnosed by ventricular strain in a population with EAS undergoing a TAVI implant, as well as study the evolution of these patterns mid-term.

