10.1 SAMPLE SIZE

Based on the information available, around 15% of the patients to whom a TAVI has been implanted show signs of amyloidosis. Mortality at two years after a TAVI is about 17% and in patients with amyloidosis, it is estimated to be 40%. Based on this data, for a significance level of 5% (error $\alpha = 0,05$) and a power of 80% (error $\beta = 0,20$), a sample size of 306 patients is estimated, assuming 5% of follow-up losses, it was decided to include 321 patients. The results in which the calculations are based are given at 2 years, if not significant; monitoring would continue up to 3 years.

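### The summary, the primary objective and the sample size each imply a different primary outcome, and no rule says which result decides the study

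*Combined protocol and SAP*

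**What the plan says.** Four places in the combined protocol and SAP bear on the primary outcome.

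- **Section 1, Study Summary, Events row:** the main event is given as a cardiovascular set (cardiovascular death, stroke, heart attack), followed by "death from any cause, readmission for cardiac insufficiency, pacemaker implantation, functional assessment". That is five items, the first of which is itself a set of three. The row has no secondary line.
- **Section 8, Primary Objective:** the two cohorts are to be compared. The text reads "compare the overall mortality and that for", and continues "cardiovascular and admissions for heart failure in the 2-year follow-up". That is three outcomes: overall mortality, cardiovascular mortality and heart-failure admissions.
- **Section 8, Secondary Objectives:** on pacing, "we will analyze separately the impact of the presence of amyloidosis on the requirements of permanent pacing", covering "permanent pacemaker implantation, pacemaker dependence, changes in the conduction system". The second secondary objective is function, measured by the 6-minute test.
- **Section 10, Sample Size:** "Mortality at two years after a TAVI is about 17"%, against an estimated 40% with amyloidosis, at a 5% significance level and 80% power. This gives 306 patients, raised to 321 for 5% losses. Results are taken at 2 years, and monitoring goes on to 3 years if they are not significant.

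The Statistical Analysis section names no primary outcome. It refers to event-free survival without saying which events count, and it uses 95% confidence intervals with no testing order or adjustment.

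**The concern.** The lists do not agree. Pacemaker implantation and function are main events in the summary and secondary in section 8. Stroke and heart attack are main events in the summary but appear in no objective. Cardiovascular mortality and heart-failure admission are primary in section 8 but were not sized.

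Two things follow. First, a favourable result on any listed outcome could be presented afterwards as the main finding, and nothing in the plan would contradict it. Second, the extension to 3 years depends on whether the 2-year result is significant. If mortality and heart-failure admission disagree at 2 years, the plan does not say whether the study continues. The ambiguity therefore affects conduct as well as reporting.

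**Working it through.** **1. Which outcomes are main, by section**

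| Outcome | Summary | Section 8 | Sample size |
|---|---|---|---|
| All-cause death | main | primary | sized (natural reading of mortality) |
| Cardiovascular death | main, within the cardiovascular set | primary | no |
| Heart-failure admission | main | primary | no |
| Stroke, heart attack | main, within the cardiovascular set | not mentioned | no |
| Pacemaker | main | secondary | no |
| Function | main | secondary | no |

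Only all-cause death is main, primary and sized.

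**2. The plan's own sample size**

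Inputs from the Sample Size section: 15% with amyloidosis, 2-year mortality 17% and 40%, alpha 5% (two-sided assumed, since sidedness is not stated), power 80%. The method is not stated. I used a log-rank calculation (Schoenfeld).

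- Hazard ratio = ln(0.60)/ln(0.83) = 2.74, so ln HR = 1.0085.
- Events = (1.960 + 0.842)² / (0.15 × 0.85 × 1.0085²) = 60.5, rounded up to 61.
- Event probability = 0.85 × 0.17 + 0.15 × 0.40 = 0.2045.
- N = 61/0.2045 = 298.3, rounded up to 299. This is within 3% of 306.
- Power at 306 (62.6 events) = 81.3%.
- Losses: 306 × 1.05 = 321.3, matching 321.

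The 306 is therefore approximately a log-rank size for mortality alone at an undivided 5%.

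**3. Chance of at least one false positive**

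Assume that no outcome truly differs between the cohorts, that each is judged two-sided at 5%, and that the test statistics are jointly normal. Independence then gives the ceiling, 1 − 0.95^m for m outcomes. Lower values use one common correlation between all pairs, by numerical integration. No document gives these correlations.

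| Correlation | 3 outcomes (section 8) | 5 outcomes (one reading of the summary) |
|---|---|---|
| 0 (ceiling) | 14.3% | 22.6% |
| 0.3 | 13.6% | 20.9% |
| 0.6 | 11.8% | 16.7% |
| 0.8 | 9.8% | 12.7% |
| 0.9 | 8.4% | 10.2% |

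**4. Cost of keeping several primary outcomes**

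If 5% were divided equally (Bonferroni), the same log-rank formula for mortality gives:

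- Three outcomes, alpha 0.0167: 81 events, N = 397 (397/0.95 = 418 with losses). Power at 306 is 67.5%.
- Five outcomes, alpha 0.01: 91 events, N = 445 (445/0.95 = 469 with losses). Power at 306 is 60.8%.

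The planned sample supports one primary outcome at 5%.

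**The case against.** The strongest reply has four parts.

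- **The summary row may not list five tests.** It has one label in the singular and could be an inventory of the events to be collected, or a single composite. Section 8 does set a hierarchy, with three primary outcomes and pacing analysed separately. This stands in part. A reader might infer five co-primary tests, but the documents do not say so, and the five-outcome figures hold only on that reading. The composite reading does not resolve the matter either: no composite is defined, a functional assessment is not an event, and no composite was sized.
- **Judging each outcome at 5% is inferred.** The only stated significance level is in the Sample Size section, for mortality; elsewhere there are 95% intervals. This stands, and the error rates are conditional on it.
- **The error rates are ceilings.** Cardiovascular death is a subset of all-cause death, so independence cannot hold. This stands too, although even at a correlation of 0.9 the three-outcome figure is 8.4%, above 5%.
- **An observational cohort need not control family-wise error.** This is a fair position for an exploratory cohort. But this plan states a directional hypothesis, fixes alpha and power, and ties the length of follow-up to significance. That rule needs a named outcome whatever view is taken of multiplicity.

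**Conclusion.** The documents disagree on the primary outcome, and the disagreement lies in the current text. For the three outcomes in the Primary Objective, the chance of at least one false positive is at most 14.3%, and about 11.8% to 8.4% at assumed correlations of 0.6 to 0.9. If the summary row is read as five separate outcomes, it is at most 22.6%. These figures assume 5% per outcome, two-sided tests and no true difference on any outcome. Separately, the 3-year continuation rule cannot be applied as written.

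Two stronger conclusions are tempting and unsupported. One is that the study has committed itself to five tests with an error rate near 23%; that takes one reading of a summary row and adds independence, which cannot hold. The other is that the sample size is wrong. The 306 is approximately reproduced for mortality alone and needs no change if mortality is the single primary outcome. Reading the unqualified term mortality in that section as all-cause is itself an inference, though the natural one.

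**What to change.** Before any outcome analysis:

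1. In sections 1, 8 and 10, name all-cause death at 2 years as the single primary outcome, tested at 5%.
2. List cardiovascular death, heart-failure admission, stroke and infarction, pacemaker implantation and function as secondary in all three sections. A fixed testing order after mortality is optional; without one, report them with intervals and no confirmatory claim.
3. State that the 2-year mortality analysis is the primary one whatever its result, and that any 3-year analysis is secondary. Without this, the extension gives the primary outcome a second, unadjusted look.
4. Say which events make up event-free survival, or remove the term.

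Cost: cardiovascular death and heart-failure admission lose primary status, which narrows the stated primary objective, so this goes beyond rewording. The target of 321 patients is unchanged, and the fix needs no extra visits or data.

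A fixed testing order across the three outcomes in section 8, or a defined composite, would also resolve the conflict. The composite would need its own sample-size calculation.

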2. GLOSSARY AND DEFINITIONS

AoS	Aortic stenosis
TAVI	Percutaneous implant of aortic prosthesis
GT99	Scintigraphy with talio ⁹⁹
PE	Protein Electrophoresis
CMR	Cardiac Magnetic Resonance
AVR	Aortic valve replacement
ECG	Electrocardiogram
6MT	6-minute test
HR	Hazard ratio
TTE	Transthoracic echocardiography
DCL	Data Collection Logbook
CREC	Clinical research ethics committee
IHC	International harmonization conference

4. INTRODUCTION AND CURRENT STATUS OF THE MATTER

The aortic stenosis.

The degenerative aortic stenosis (AS) is a progressive disease that is related to atherosclerosis, inflammation, hemodynamic factors, and active calcification. Its prevalence is high and depends on age. More than 3% of people over 75 have aortic stenosis(1) and reaches 8% in people over 84(2). When symptoms appear, the disease is rapidly progressive, and a surgical or percutaneous aortic valve replacement is necessary. It is, therefore, a disease with a major impact on society. Without a doubt, we are facing a serious health problem that will increase in the future, giving the aging population.

The percutaneous implantation of an aortic valve prosthesis.

Given the nature of the degenerative aortic stenosis, most of the patients affected to a severe degree and requiring treatment have an advanced age. The fragility of aging combined with the comorbidities presented in many cases makes up one-third of the patients who are not candidates for a surgical valve and another third present a high risk. The percutaneous implantation of an aortic prosthesis (TAVI) emerges as a less invasive alternative for the treatment of aortic stenosis. The randomized study PARTNER demonstrated in cohort B a reduction in mortality with this technique compared with standard medical treatment in inoperable patients(3). In cohort A of the PARTNER study, no differences were found in the survival of patients with high-risk surgical treatment randomized to conventional surgery or percutaneous implant(4). The studies PARTNER-II and SURTAVI have more recently shown that those patients, with intermediate surgical risk, the percutaneous aortic prosthesis implant has similar results to those of conventional surgery (5)(6). This has increased the number of percutaneous aortic prosthesis implants exponentially.

There are still many doubts about the long-term outcome after a TAVI implant. Avoiding the sternotomy and extracorporeal circulation by means of a percutaneous access has many advantages, but it also causes a series of technical and clinical problems: 1, cerebrovascular events, not only those due to the handling of large

vessels during the procedure but also those occurred in the monitoring where there is still no solid evidence regarding antithrombotic handling. 2, Atrioventricular conduction disorders requiring permanent pacemaker implantation in 20-40% of the patients. 3, Vascular complications of the accesses. 4, Residual valve by the malpositioning of the prosthesis (creating a high residual gradient or insufficiency). 5, Valvular degeneration and durability of the prosthesis.

Cardiac amyloidosis by transthyretin.

The amyloid myocardial infiltration by transthyretin monomers and oligomers (TTR) with misfolding(7) is a serious and under-diagnosed disease which predominantly affects men over 60 years old and presents itself with symptoms of heart failure, orthostatic hypotension, and syncope (8). The infiltration of the cardiac conduction system can generate branch blocks, atrioventricular blocks, and atrial fibrillation.

There are two types of amyloid that can infiltrate the myocardium: the amyloid light chain (AL or primary) within a monoclonal gammopathy, and the TTR amyloid. The latter in turn has two types of disease, familial, due to a mutation that causes transthyretin misfolding; and sporadic (formerly known as senile), which is due to incorrect folding of the common transthyretin. (8)

The prevalence of the TTR amyloidosis in patients with AoS to whom a TAVI is performed is estimated at 14-16%(9)(10) and 6% in those over 65 years old to whom a surgical valve replacement is performed(11). It is especially associated with the AoS phenotype of low-flow and low gradient (9). Cardiac amyloid deposits were found in nearly one-third of autopsies of patients with TAVI implants who died before 30 months(12), and the patients with AoS and amyloidosis have a prognosis similar to those with amyloidosis without AoS (13). It all states that the amyloidosis implies a worse prognosis (11). It is also suggested that amyloid infiltration may increase the requirements of permanent pacing (14).

Recently the benefits of treatment with Tafamidis on patients with cardiac amyloidosis by TTR have been published. (15)

Non-invasive diagnosis of cardiac amyloidosis.

The echocardiogram is used to find interesting data of amyloidosis: increased thicknesses of the atrioventricular valves, interatrial septum valves or the free wall of

the right ventricle, the light pericardial effusions, high atrial dilation, a birefringence characteristic (*sparkling*) and a speed of S' waveform mitral in the *Doppler* tissue lower than 6cm/s(9), but in no case is it diagnosed. The mechanical ventricular assessed by *speckle tracking*(tracking marks) may be useful in monitoring patients with amyloidosis as there seems to be a link between the longitudinal *strain* of the ventricular and the cardiac involvement (16). The longitudinal *strain* is decreased in the basal and middle segments and stored in the apical segments(17). This typical pattern helps obtain the differential diagnosis with other causes of hypertrophy ventricular, with high sensitivity and specificity (90-95% and 80-85%, respectively). The value of the strain is also an independent prognostic factor (18).

The maps on T1 MRI may have a role in the diagnosis (19), but it is still a technique in the early stage of development.

Until recently, the diagnosis of amyloidosis required histological confirmation by biopsy and staining with Congo red of the sample. Recent studies have demonstrated the diagnostic capacity of the pyrophosphate tecnecio⁹⁹ scintigraphy (20), with a sensitivity of more than 99% and a specificity of 86% for the TTR amyloidosis, being false positives due almost exclusively to the presence of AL amyloidosis. Therefore, the caption of radiotracer in grades 2 o 3 together with the absence of a monoclonal protein in the electrophoresis has a specificity and a positive predictive value to 100% TTR amyloidosis. (21)

7. HYPOTHESIS

Amyloidosis is a disease which coexists in a high percentage of patients referred for TAVI by severe aortic stenosis; the pathophysiological mechanisms of this relationship have a negative impact on prognosis.

8. OBJECTIVES

8.1 PRIMARY OBJECTIVE

A multicentre prospective study of cohorts consisting of two cohorts from patients who have been implanted with percutaneous aortic prosthesis as treatment for the severe degenerative aortic stenosis and compare the overall mortality and that for

cardiovascular and admissions for heart failure in the 2-year follow-up of patients diagnosed with amyloidosis (by GT99 and EFP) versus those that do not have it.

8.1 SECONDARY OBJECTIVES

1. As part of the hypothesis, we will analyze separately the impact of the presence of amyloidosis on the requirements of permanent pacing (permanent pacemaker implantation, pacemaker dependence, changes in the conduction system)
2. Determine the impact on the functional class (measured by using the 6-minute test) of the coexistence of TTR amyloidosis in patients with a TAVI implant.
3. Validate echocardiographic patterns of cardiac amyloidosis diagnosed by ventricular strain in a population with EAS undergoing a TAVI implant, as well as study the evolution of these patterns mid-term.

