9. DESIGN

A multicentre, analytical, observational study of two cohorts. One cohort will be constituted by the patients to whom a TAVI will be implanted, and that meet non-invasive diagnostic criteria of TTR amyloidosis (capturing of radiotracer in grades 2 and 3 and absence of monoclonal gammopathy the PE of urine or serum). The other cohort will be constituted by patients whose TAVI implants do not meet the diagnostic criteria for TTR amyloidosis.

A clinical and echocardiographic follow-up will be done in all patients for two years.

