10. STATISTICAL ANALYSIS PLAN AND SAMPLE SIZE

10.1 STATISTICAL ANALYSIS

A descriptive analysis of both cohorts defining their clinical and angiographic profiles and a comparative study of the two groups (cohorts) will be performed. The categorical variables are expressed in percentages and the continuous as medium value \pm standard deviation. The relative risk and the “Hazard Ratio” will be used as measures of effect when variables are analyzed with a temporal component, always with a confidence interval of 95%. For the comparison of categorical variables, the Chi-square or the Fisher test will be used. To compare continuous variables, the “t” of student test or analysis of variance will be used. The variables of time to event, such as the analysis of event-free survival will be analyzed by using the Kaplan- Meier technique and will be supplemented by the log-rank test. The multivariate analysis of the adverse events predictors during the follow-up will be done by means of the Cox regression model, determining the Odds Ratio for each variable.

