11. PATIENTS FOLLOW-UPS

11.1 INITIAL PATIENT ASSESSMENT

An initial inclusion visit will assess whether the patient is a candidate who meets the inclusion criteria and none of the exclusion ones. After being informed, if they accept, the informed consent must be signed. The following data must be recorded:

- **Clinical parameters:** age, sex, height, weight, body mass index, body surface, cardiovascular risk factors, medication intake, background interests, history of heart disease, presence of ischemic heart disease, cerebrovascular accident, peripheral artery disease, chronic obstructive pulmonary disease, symptoms (angina, syncope, dyspnea according to grades of the NYHA, other symptoms), blood pressure, heart rate, evidence of heart failure, assessment of functional class by means of 6MT and fragility assessment.
- **Analytical parameters:** hematocrit, NT-proBNP, Troponin I, electrolytes, C-reactive protein, creatinine, glomerular filtrate.
- **Protein electrophoresis:** Rating presence of the monoclonal component
- **Scintigraphy with TC⁹⁹:** Assessment of values of tracer uptake.
- **Device parameters:** Type of prosthesis, dimensions, expandable/ self-expanding ball, post-dilatation.
- **ECG parameters:** Rhythm, PR duration, pacemakers, implantable cardioverter defibrillator, QRS duration.

- The 6 minute-test: All patients in the study will have a test of 6 minutes before implantation and 6 months follow-up, according to the protocol after a TAVI, in order to carry out an objective functional assessment of the functional capacity. The distance covered will be determined, the variation of oxygen saturation by means of non-invasive pulse oximetry before and after the test and the appearance of symptoms with the effort according to the Borg scale.

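### The pacing objective has no at-risk set for new pacemaker implantation and no handling of death as a competing event, although assumed 2-year mortality is 40% v 17%

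*Combined protocol and SAP*

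**What the plan says.** Section 8.1 (Secondary objectives) sets out to study the effect of amyloidosis on pacing needs: "permanent pacemaker implantation, pacemaker dependence, changes in the conduction system". Pacemaker implantation is also among the events in the Study Summary. Neither place gives a denominator or a time point.

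Section 9.3 has four exclusions: in-hospital death from a procedural complication, mitral disease needing intervention, valve-in-valve implants and lack of consent. None concerns a prior pacemaker. Section 11.1 records ECG parameters at the initial assessment ("Rhythm, PR duration, pacemakers, implantable cardioverter defibrillator, QRS duration"), but no rule says how a prior pacemaker enters the analysis.

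Section 10.1 (Statistical analysis) says that variables of time to event, "such as the analysis of event-free survival will be analyzed" by Kaplan-Meier with the log-rank test. Cox regression is named for predictors of adverse events, and chi-square or Fisher for categorical variables. Pacing is not assigned to any of these, and no competing-risk method appears.

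The sample-size section states "Mortality at two years after a TAVI is about 17% and in patients with amyloidosis, it is estimated to be 40" (per cent), and that "around 15% of the patients to whom a TAVI has been implanted show signs of amyloidosis". Section 9 adds: "A clinical and echocardiographic follow-up will be done in all patients for two years".

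**The concern.** There are two separate gaps.

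- **Who is at risk.** A patient paced before TAVI cannot contribute a new implantation. Section 4 says that infiltration of the conduction system can cause branch and atrioventricular block, so prior pacing may differ between cohorts. If so, an all-patient denominator distorts the comparison.
- **What happens at death.** A patient who dies unpaced can no longer be paced. Kaplan-Meier with deaths censored estimates the risk as if death did not occur, which is higher than the proportion actually paced. With very different mortality in the two cohorts, the overstatement is unequal.

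At stake is whether the reported pacing incidences, and the ratio or difference between them, can be read as the effect of amyloidosis. With the denominator undefined, it could also be settled after the data are seen.

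**Working it through.** **Inputs from the documents.** Two-year mortality of 40% (amyloid) and 17% (stated for TAVI generally, used here for the other cohort); 15% amyloid prevalence; 306 patients; 2 years of follow-up. Section 4 gives permanent pacing in 20-40% after TAVI, not split by cohort.

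**Assumptions.** Net pacing risks and hazard ratios, timing of implants, and prior pacing rates are mine; the plan gives none by cohort. Hazards are constant unless stated, and the death hazard is taken as unaffected by pacing.

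**Step 1: the plan's own figure.** The plan states "a sample size of 306 patients is estimated, assuming 5% of follow-up losses, it was decided to include 321 patients". The death hazards are −ln(0.60)/2 = 0.2554 and −ln(0.83)/2 = 0.0932 per year, a ratio of 2.74. Schoenfeld's formula (two-sided 5%, 80% power) gives 7.85/(0.15 × 0.85 × (ln 2.74)²) = 60.5, so 61 events. Mean mortality is 0.85 × 0.17 + 0.15 × 0.40 = 0.2045, and 61/0.2045 gives 299 patients, 2.3% below 306. Then 306 × 1.05 = 321.3. The mortality figures can therefore be carried forward as the planning assumptions. This calculation concerns mortality; none is given for pacing.

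**Step 2: Kaplan-Meier against cumulative incidence.** With pacing hazard λp and death hazard λd:

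- one minus Kaplan-Meier = 1 − exp(−2λp)
- cumulative incidence = λp/(λp + λd) × [1 − exp(−2(λp + λd))]

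For net risks of 35% (amyloid) v 25% (other):

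- Amyloid: λp = −ln(0.65)/2 = 0.2154; 0.2154/(0.2154 + 0.2554) × (1 − 0.65 × 0.60) = 0.4575 × 0.61 = 27.9%.
- Other: λp = −ln(0.75)/2 = 0.1438; 0.1438/(0.1438 + 0.0932) × (1 − 0.75 × 0.83) = 0.607 × 0.3775 = 22.9%.

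| Scenario | Kaplan-Meier, amyloid v other | Ratio | Cumulative incidence, amyloid v other | Ratio |
|---|---|---|---|---|
| Net 25% v 25%, constant | 25.0% v 25.0% | 1.00 | 19.8% v 22.9% | 0.86 |
| Net 35% v 25%, constant | 35.0% v 25.0% | 1.40 | 27.9% v 22.9% | 1.22 |
| Net 30% in other, hazard ratio 1.5, constant | 41.4% v 30.0% | 1.38 | 33.2% v 27.5% | 1.21 |
| Same, 85% of the pacing hazard in the first 30 days | 41.4% v 30.0% | 1.38 | 40.0% v 29.6% | 1.35 |

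In the first row Kaplan-Meier overstates incidence by 5.2 points with amyloidosis and 2.1 points without. In the second, the apparent risk difference is 10.0 points against 5.0.

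**Step 3: already paced patients in the denominator.** If a fraction b is paced beforehand, the all-patient risk is (1 − b) times the at-risk risk, so the observed ratio is the true ratio × (1 − b_amyloid)/(1 − b_other). With an assumed true ratio of 1.50 (new-implant risk 30% v 20%):

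- prior pacing 20% amyloid v 10% other: 1.50 × 0.80/0.90 = 1.33
- 10% v 10%: 1.50 × 0.90/0.90 = 1.50; the risk difference falls from 10 points to 27 − 18 = 9
- 10% v 15%: 1.50 × 0.90/0.85 = 1.59

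**The case against.** A reader might infer that the plan counts every patient in the pacing analysis, applies Kaplan-Meier to it, and is therefore biased towards no effect. The documents do not support that.

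- **Silence is not a choice.** No denominator is stated, and pacing is not tied to Kaplan-Meier by name. A chi-square comparison of periprocedural implants would also fit Section 10.1. This stands: the fault is an undefined at-risk set, together with a general time-to-event method that leaves death unaddressed.
- **The direction for Kaplan-Meier is the opposite.** Censoring deaths inflates the higher-mortality cohort more, so it exaggerates an amyloid excess. This stands, as Step 2 shows.
- **Dilution is conditional.** It needs more prior pacing in the amyloid cohort. Section 4 makes that plausible but gives no rate, and the reverse imbalance moves the ratio the other way.
- **Timing may make the competing risk minor.** Section 4 lists pacing among the problems of the percutaneous procedure. If most implants are early, 1.38 becomes 1.35 rather than 1.21. This stands.
- **Part of the plan is already adequate.** Log-rank and Cox with deaths censored validly compare cause-specific hazards. Pacemaker dependence can be assessed in patients already paced, so enrolling them is not an error.
- **The objective is secondary and has no stated power.** For a ratio of 1.5, a 20% risk in the other cohort, 306 patients and prior pacing of 20% v 10%, power is about 30% in at-risk patients and 18% in all patients. This limits the consequence but does not remove the need for a defined estimate.

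**Conclusion.** The point holds in this form. Already paced patients can enrol and nothing removes them from the new-implant analysis. The plan's general time-to-event approach has no provision for death, at assumed mortality of 40% v 17%.

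Censoring deaths would exaggerate the amyloid excess in absolute risk: 1.40 against 1.22 under constant hazards with net risks of 35% v 25%, and much less if implants cluster around the procedure. An all-patient denominator would lower incidence in both cohorts; the ratio could fall to 1.33, stay at 1.50 or rise to 1.59, depending on prior pacing rates that the plan does not give.

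The two effects can oppose each other, so no net direction can be claimed. The cause-specific hazard comparison by log-rank or Cox is not in doubt. The remedy is the same whichever effect dominates, so the change should be made.

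**What to change.** In Sections 8.1 and 10.1:

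1. Define new permanent pacemaker implantation among patients without a pacemaker before TAVI, and report prior pacing by cohort.
2. State that the pacemaker status in Section 11.1 means status before TAVI. Section 13.1 has baseline variables collected before discharge. A status taken after the procedure could count a new implant as a prior one and remove the event itself.
3. For this event, replace Kaplan-Meier with cumulative incidence treating death as a competing event, and report the cause-specific hazard ratio beside it.
4. Keep pacemaker dependence as a separate outcome that can be assessed in all patients.

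For the conduction component, Section 11.2 lists an ECG at baseline and 12 months, while the Work Plan table adds 6 months and 2 years. These passages must be reconciled.

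The cost is SAP wording, a little more analysis and a slightly smaller denominator. Pacemaker status is already collected; only its timing needs stating.
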